12 STATISTICAL METHODS AND PLANNED ANALYSES

12.1 Sample size estimation

A sample size of 100 subjects per treatment group will provide 80% power to detect a difference of 16% in median percent reduction in seizure frequency between an active dosage group and placebo group, at a 2-sided significance level of 0.05, assuming a standard deviation of 40%.

12.2 Statistical Methods

Summary statistics and analyses will be presented by the treatment group category assigned to the subject regardless of the dosage of drug administered. Categorical variables will be summarized as frequencies and percentages. Descriptive statistics for continuous variables will include sample size, mean, median, standard deviation, and minimum and maximum values. SAS[®] version 9.2 or later will be used for all data summaries, statistical analyses, and data

listings. Inferential statistical tests will be 2-sided and will employ a tolerance for type I error (alpha, α) of 0.05. Data will be used as collected. Full details of the analysis plan will be included in the Statistical Analysis Plan (SAP) and finalized prior to any un-blinding of efficacy data.

Analyses of Missing Data

The primary efficacy endpoint definition in the United States and Rest of the world states that seizure rates will be calculated using days with non-missing seizure data. The definition does not explicitly account for days with missing data, i.e., days during which the presence or absence of seizures was not recorded in personal diaries. However the definition implicitly accounts for missing data in that it is identical to a definition in which days with missing data are assumed to have the same seizure rate as days with non-missing data.

Similar to the United States definition of the primary efficacy endpoint, the primary endpoint (responder) definition in the countries of Europe, Australia, New Zealand and South Africa implicitly accounts for missing data during maintenance phase in that it is identical to a definition in which days with missing data are assumed to have the same seizure rate as days with non-missing data. An additional analysis will be performed in which subjects who dropped out during the titration phase will be included in the analysis by having their maintenance phase data imputed using the available titration data.

The same approach will be used for missing data in the analysis of all secondary efficacy endpoints.

12.3 Analysis Data Sets

For all populations, subjects will be analyzed according to the target (randomized) dosage group including subjects who fail to achieve the target dosage during the titration phase.

Enrolled subjects: All subjects who have given informed consent to participate in this study will be considered enrolled subjects.

Intention-to-treat (ITT): All randomized subjects will be considered intention-to-treat subjects.

Modified intention-to-treat (MITT) subjects: All randomized subjects who have taken at least one dose of YKP3089 (or placebo) and have any post-baseline seizure data will be considered modified intention-to-treat subjects.

Modified intention-to-treat (MITT-M) subjects in Maintenance phase: All randomized subjects who have completed the titration phase and have taken at least one dose of YKP3089 (or placebo) in the maintenance phase and have any maintenance phase seizure data will be considered modified intention-to-treat subjects in the maintenance phase.

Per protocol population (PP): All randomized subjects who have no major protocol violations and have at least 80% drug compliance will be considered per-protocol subjects.

Safety evaluable subjects (SE): All ITT subjects.

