12.8 Safety Variable Analyses

All ITT subjects will be evaluable for safety. The number and percent of subjects reporting AEs (including treatment-emergent laboratory abnormalities) will be tabulated by randomized treatment group. All serious AEs (SAEs) will be tabulated separately as well as included with all reported AEs.

Physical and neurologic assessments, laboratory results, vital signs (including orthostatic measurements), ECGs, and C-SSRS will be summarized using descriptive statistics.

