8 STUDY PATIENTS

8.1 Analysis Population

Open-Label Extension Safety Evaluable Population (OLE-SE): All subjects treated in DB who continued into OLE phase and took at least one dose of open-label study medication. All OLE safety analysesdescribed in this SAP will be performed using OLE-SE.

Open-Label Extension Efficacy Analysis Population(OLE-EA): All subjects who entered in OLE phase, took at least one dose of open-label medication and have any seizure data recorded in OLE seizure diary. All OLE efficacy analyses descried in this SAP will be performed by OLE-EA

Double-Blind and Open-Label Extension Safety Evaluable Population: All subjects who received at least one dose of study medication in either DB period only (ie, subjects treated in DB who did not continue in OLE phase) or in both DB and OLE (ie, subjects included in OLE-SE population). This analysis population will be considered when reporting protocol deviations.

OLE analysis summary results will be presented by the following treatment groups:

- All YKP3089 OLE
- YKP3089 100mg DB to YKP3089 OLE
- YKP3089 200mg DB to YKP3089 OLE
- YKP3089 400mg DB to YKP3089 OLE

Placebo DB to YKP3089 OLE,

where YKP3089 100mg, 200mg, 400mg DB, and Placebo DB represent the randomized treatment group in double blind period and YKP3089 OLE represents the treatment given during OLE.

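### The protocol's double-blind safety set has no dosing condition and is tabulated as randomised, so never-dosed and wrongly treated subjects can distort adverse-event rates

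*Protocol*

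**What the plan says.** Protocol Section 12.3 gives the safety set as "Safety evaluable subjects (SE): All ITT subjects" and defines ITT without a dosing condition: "All randomized subjects will be considered intention-to-treat subjects". The same section fixes the grouping: "For all populations, subjects will be analyzed according to the target (randomized) dosage group", and this extends to subjects who do not reach their target dose.

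Section 12.8 repeats both choices. "All ITT subjects will be evaluable for safety", and adverse events "will be tabulated by randomized treatment group". Section 12.2 is in line with this: results are "presented by the treatment group category assigned to the subject regardless of the dosage of drug administered". The protocol contains no dosed-only or as-received double-blind safety analysis.

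Two other parts of the protocol sit differently. Section 6.3 describes double-blind safety as a comparison of YKP3089-treated with placebo-treated subjects. And in Section 12.3 itself the MITT efficacy set requires at least one dose, while the safety set does not.

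The supplied SAP covers the open-label extension. Its Section 8.1 includes a combined double-blind and extension set that begins "All subjects who received at least one dose of study medication in either DB period only" and goes on to subjects dosed in both periods. The SAP assigns that set to the reporting of protocol deviations.

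**The concern.** Safety and tolerability is the trial's other stated objective (protocol Section 5). There are two ways in which the rule can distort it.

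- **Never dosed.** Drug is dispensed at randomisation (Section 9.1.3) and by default the first dose is taken the following morning, so a subject can be randomised and never dosed. That subject cannot have a treatment-emergent event but still counts in the denominator.
- **Wrong treatment.** Tablets look identical, there are nine card types (Section 8.1.1), and cards are issued repeatedly. SAP Appendix 1 lists incorrect dose taken and randomisation not followed among its predefined deviations. The protocol has no rule for placing such a subject by treatment received.

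Percentages are not the only thing at stake. Section 4.6 reports a hypersensitivity case consistent with DRESS, judged probably related to YKP3089. One such event in a subject randomised to placebo but given active drug in error would be tabulated under placebo. In a dose-response trial, a single serious event in the wrong column can matter more than a dilution of one or two percent.

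**Working it through.** **The plan's own figure.** The only sample-size statement (Section 12.1) is 80% power with 100 per group, a difference of 16, SD 40 and 2-sided alpha 0.05. The standardised difference is 16 / (40 × √(2/100)) = 2.828, and Φ(2.828 − 1.960) = 0.807, so it reproduces (99 per group are needed for 80%). Nothing below depends on it. It is used only for the arm size of 100.

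**Inputs not in the documents.** The numbers never dosed (k) and misallocated (m) and the adverse-event rates are not given. Assumed ranges: k and m from 0 to 5 per arm of 100, with rates of 40% on active and 20% on placebo.

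**Never-dosed subjects.** If they contribute no treatment-emergent events, reported rate = true rate × (100 − k)/100.

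| k per arm | 40% reported as | 20% reported as | Difference (points) |
|---|---|---|---|
| 0 | 40.0% | 20.0% | 20.0 |
| 1 | 39.6% | 19.8% | 19.8 |
| 2 | 39.2% | 19.6% | 19.6 |
| 5 | 38.0% | 19.0% | 19.0 |

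With equal k the risk ratio does not move: 38.0/19.0 = 40/20 = 2. With unequal k the difference can go either way: 5 undosed on active only gives 38 − 20 = 18 points, and 5 undosed on placebo only gives 40 − 19 = 21 points.

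**Misallocated subjects.** With m subjects swapped each way for the whole period and tabulated as randomised, active = [(100 − m) × 40 + m × 20]/100 and placebo = [(100 − m) × 20 + m × 40]/100.

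| m each way | Active | Placebo | Difference (points) |
|---|---|---|---|
| 0 | 40.0% | 20.0% | 20.0 |
| 1 | 39.8% | 20.2% | 19.6 |
| 2 | 39.6% | 20.4% | 19.2 |
| 5 | 39.0% | 21.0% | 18.0 |

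The active rate falls, the placebo rate rises and the difference shrinks.

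**After the change.** With a denominator of dosed subjects (100 − k), the 38.0% at k = 5 returns to 40.0%. With fully misallocated subjects grouped by treatment received, the 18.0 points at m = 5 return to 20.0.

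**The case against.** The strongest case on the other side is that the effect is negligible. Subjects are randomised after an 8-week baseline, receive drug at that visit and start the next morning or on site, so none or one undosed per arm is quite compatible with the documents. Even k = 5 shifts a 40% rate by 2 points, against a standard error of √(0.4 × 0.6/100) = 4.9 points. Numerators are untouched by dilution, Section 12.8 reports counts as well as percentages, and SAP Section 8.3 lists deviations from both periods. All of this stands and limits the weight of the point.

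Section 12.8 is also not worded as treatment-emergent events only, apart from laboratory abnormalities. Adverse events are recorded from Visit 2, so an undosed subject could have a counted event. Section 6.3 does speak of treatment-emergent events. The dilution formula therefore holds for treatment-emergent rates and not necessarily for every row of a 12.8 table.

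A wrong weekly card is typically one week in 18, and a bare as-received rule would not say where that subject belongs. This is fair, and the fix has to answer it. Keeping subjects who miss their target dose in their randomised group is ordinary practice and no fault.

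Three stronger readings are tempting, and the documents do not support them.

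- A reader might infer that the SAP contradicts Section 12.3 because its combined set requires a dose. That set belongs to an extension plan and is named for protocol deviations, so it does not redefine the double-blind safety set.
- A reader might infer that every rate moves toward zero. Misallocation raises the lower rate, from 20% to 21% at m = 5.
- A reader might infer that the rule can never err on the conservative side. Unequal undosed numbers can widen a difference, as the 21-point case shows.

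**Conclusion.** The point holds for the protocol text. Sections 12.2, 12.3 and 12.8 consistently describe a double-blind safety analysis of all randomised subjects, as randomised, and that does not match the treated-versus-treated comparison in Section 6.3. Followed literally, never-dosed subjects enlarge the denominators, and subjects treated throughout under another assignment are counted in an arm not received. The tendency is to shrink active-placebo differences, though not in every configuration.

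On the assumed range of 0 to 5 per 100, a 40% treatment-emergent rate is understated by 0 to 2 points and a 20-point difference by 0 to 2 points under swapping. If nobody is undosed or misallocated there is no effect. This is a worthwhile correction to a stated rule and poses no threat to the trial's conclusions. One limit remains: Section 12.2 defers full details to the SAP, and SAP Section 6 refers to a separate double-blind SAP. That document was not supplied and may define the set differently.

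**What to change.** - In Section 12.3, define the safety evaluable set as all randomised subjects who took at least one dose of YKP3089 or placebo.
- Group them by randomised target dose, including subjects who miss or reduce from target and those with an isolated wrong card. The exception is a subject who received a different treatment assignment for most of the dosed double-blind period, who is grouped by the treatment received.
- Change Section 12.8 to match, so that both sections agree with Section 6.3, and qualify the as-assigned sentence in Section 12.2 for safety.
- List never-dosed and misallocated subjects separately.
- Confirm that the double-blind SAP uses the same definition.

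The cost is a few sentences of text. No new data are needed, and no sample-size or efficacy figure changes.

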12.4 Baseline Comparability

All demographic measurements (age, gender, height, and weight) and all safety measurements (ECGs, vital signs, and clinical laboratory values) will be summarized by dose level.

12.5 Primary Efficacy Analyses

12.5.1 Primary Efficacy Analysis in the United States and the Rest of the World:

The primary efficacy analysis of the primary endpoint will be based on the MITT population.

The testing strategy for the primary efficacy endpoint (percent change in seizure frequency) is to compare each of the YKP3089 dosage groups with the placebo group. Due to multiple treatment comparisons, a step-down procedure will be used to ensure the overall type I error rate is controlled at the 5% level. Each of the YKP3089 dosage groups will be compared with the placebo group according to the following hierarchy:

1. 200-mg dosage group versus placebo group
2. 400-mg dosage group versus placebo group
3. 100-mg dosage group versus placebo group

The 200-mg dosage group will be compared with the placebo group at a 2-sided 0.05 level as the first step. If no statistically significant difference is detected between the 200-mg dosage group and the placebo group, the procedure will stop and it will be concluded that none of the YKP3089 dosages are efficacious. If a statistically significant difference is detected between the 200-mg dosage group and the placebo group in favor of the 200-mg dosage group, the procedure will proceed to the next step to compare the 400-mg dosage group with the placebo group at a 2-sided 0.05 level. If a statistically significant difference is detected between the 400-mg dosage group and the placebo group in favor of the 400-mg dosage group, the procedure will proceed to the next step to compare the 100-mg dosage group with the placebo group at a 2-sided 0.05 level.

An analysis of covariance (ANCOVA) model will be fit to the ranked values of the primary efficacy endpoint. The ANCOVA will have terms for ranked baseline seizure rate and randomized treatment group. Ties will be handled using the default option in SAS

It should be noted that the primary efficacy analysis uses a non-parametric approach. Because of this, effect sizes are not estimated and tested directly, since testing is made on the rank of the primary efficacy value. However, summary tables for the actual (not the ranked) primary efficacy endpoint will be presented.

Descriptive results of the primary efficacy end point will be provided for the subjects who were titrated under the original protocol.

12.5.2 *Primary Efficacy Analyses in the countries of Europe, Australia, New Zealand, and South Africa*

The primary efficacy analysis of the primary endpoint will be based on the MITT-M population.

The testing strategy for the primary efficacy endpoint (responder rate) is to compare each of the YKP3089 dosage groups with the placebo group. A step-down procedure will be used to ensure the type I error rate due to multiple treatment comparisons is controlled at the 5% level. Each of the YKP3089 dosage groups will be compared with the placebo group according to the following hierarchy:

1. 200-mg dosage group versus placebo group

2. 400-mg dosage group versus placebo group
3. 100-mg dosage group versus placebo group

The 200-mg dosage group will be compared with the placebo group at a 2-sided 0.05 level as the first step. If no statistically significant difference is detected between the 200-mg dosage group and the placebo group, the procedure will stop and it will be concluded that none of the YKP3089 dosages are efficacious. If a statistically significant difference is detected between the 200-mg dosage group and the placebo group in favor of the 200-mg dosage group, the procedure will proceed to the next step to compare the 400-mg dosage group with the placebo group at a 2-sided 0.05 level. If a statistically significant difference is detected between the 400-mg dosage group and the placebo group in favor of the 400-mg dosage group, the procedure will proceed to the next step to compare the 100-mg dosage group with the placebo group at a 2-sided 0.05 level.

The data will be summarized using frequencies and percents of subjects achieving at least a 50% response to treatment, the responder rate. The responder data will be analyzed using a chi-square test.

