In the Phase 2a study, 113 subjects received YKP3089 and 109 received placebo. Comparison of the primary efficacy endpoint, median percent reduction in partial seizure frequency, demonstrated a highly statistically significant effect in favor of the YKP3089 group, 55% vs 21%, $p < 0.0001$. Initial efficacy was observed at doses of 50-100mg/day and maintained throughout the 12 week study. Review of the safety data indicated that 4% of subjects in the active and 4% of subjects in the placebo-group dropped out because of adverse events. Two-thirds of subjects completed the study at the target dose of 200mg/day. The most common central nervous system adverse events in the YKP3089 group were somnolence, dizziness, fatigue, and gait disorder.

Two suspected unexpected serious adverse reaction (SUSAR) occurred in YKP3089 treated subjects: an early manifestation of a drug hypersensitivity reaction characterized by flushed

erythema of palms and soles with mild itching of ears and a status epilepticus during tapering. During the open-label extension, 2 notable serious adverse events occurred in YKP3089 treated subjects: one case of sudden unexpected death in epilepsy (SUDEP) and one case of suicide. They were considered remotely related or unrelated to study drug.

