5 STUDY OBJECTIVES

The **primary** objective of this study is to determine the effective dose range of YKP3089 as adjunctive therapy for the treatment of partial seizures.

The trial will also evaluate the safety and tolerability of YKP3089 in the partial epilepsy population.

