13.6 Protocol Amendments

Protocol Amendments will not be implemented without agreement from the Sponsor and prior submission to and written approval from the Institutional Review Board, except when necessary to eliminate an immediate hazard to the subject.

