 - a. The blinded 2-week crossover period (for subjects participating in the open-label extension), during which all subjects will be converted to a target dose of 300 mg once daily, of open-label YKP3089. During the first week of the conversion period, the investigator can increase or decrease the open-label dosage by 50-100 mg if clinically indicated. During the second week of the conversion period, the investigator can decrease the open-label dosage by 50-200 mg or increase the open label dosage by a maximum of 100 mg if clinically indicated.

- b. The open-label extension period: Refer to section 6.1.4.2 of the protocol for details on the open label extension.
- c. The taper period of 3 weeks with a final follow-up visit 2 weeks after the last dose of study drug. Refer to section 6.1.4.3 of the protocol for details and the table for taper period.

Figure 1 Study Flowchart

Study assessment chart for double-blind period is included in DB SAP. OLE SAP includes details for study assessment chart for OLE only.

Table 1 Study Assessment Flow Chart for Open-Label Extension Phase

Visit windows of ± 3 days allowed for Visits 9 and Visit 17 (end of study follow-up visit)				Treatme	nt		End of Study Follow-up		
Visit windows of ± 2 days allowed for Visits 11 and 12. Visit windows of ± 7 days allowed for all other open-label visits	Visit 9 First Day of	Visit 11	Visit 12	Visit 13	Visit 14		Visit 16 or Terminati on Visit	Post 1 year	Visit 17
Assessment	Day 127ª	Day 141	Day 155	Day 239	Day 323	Day 407	Day 491	Every 3 months ^b	14 days after the last dose
Inclusion/exclusion ^c	Х								
Vital signs ^d	Χ	Х	Х	Х	Х	Х	Х	Х	Х
Weight	Χ			X		Χ	Х	Xe	Х
Full physical examination	Χ						Х	X ^f	
Full neurologic examination	Х						Х		Х
Brief neurologic exam		X		X		Χ		Xe	
C-SSRS ^g	Χ	X	X	X	X	X	Х	Χ	Х
ECG ^h	Χ		X				X	X ^f	

Serum pregnancy test ⁱ									Х
Urine pregnancy test ⁱ	Х		Х		Х		Х	Xe	
Laboratory safety assessment ^j	Х		Х		Х		Х	Xe	Х
Urinalysis	Х				Х		Х	X ^f	Х
Concomitant medication	Х	Х	Х	Х	Х	Х	Х	Х	Х
Dispense/review/ collect seizure diary	Х	Х	Х	Х	Х	Х	Х	Х	
Drug accountability	Х	Х	Х	Х	Х	Х	Х	Х	Х
Dispense study drug	Χ	Х	Х	Х	Х	Х	Х	Х	
Adverse events	Х	Х	Х	Х	Х	Х	Х	Х	Х

C-SSRS = Columbia Suicide Severity Rating Scale; ECG = electrocardiogram; AED = antiepileptic drug.

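### If 200 mg misses significance, the protocol concludes that no dose works; the stopped sequence supports only that no dose can be claimed on that primary endpoint

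*Protocol*

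**What the plan says.** The protocol has two primary families. Section 12.5.1 (United States and Rest of the World) tests percent change in seizure frequency over the double-blind period in the MITT population by rank ANCOVA. Section 12.5.2 (Europe, Australia, New Zealand, South Africa) tests the 50% responder rate in the maintenance phase in the MITT-M population by chi-square. Each compares 200 mg, then 400 mg, then 100 mg with placebo at two-sided 0.05, moving on only after a significant result in favour of the dose just tested. The stated purpose is control of type I error at 5%.

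In both families, if the 200 mg comparison is not significant, "the procedure will stop and it will be concluded that none of the YKP3089 dosages are efficacious". The same sentence stands in the two corresponding entries of the synopsis (Section 1, Statistics and analyses), so it appears four times in the current text.

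The primary objective in Section 5 is "to determine the effective dose range of YKP3089 as adjunctive therapy". On where the detail sits, Section 12.2 says: "Full details of the analysis plan will be included in the Statistical Analysis Plan (SAP"). The supplied SAP covers the open-label extension only and plans no inferential analysis (Section 11.1). Its Section 6 points to a separate document: "Study assessment chart for double-blind period is included in DB SAP". That document was not supplied.

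**The concern.** A fixed-sequence test decides which null hypotheses may be rejected while the error rate is held. If the first is not rejected, none may be. The protocol goes further and prescribes a negative finding on every dose. That finding fails in two ways.

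- For 200 mg, it treats a non-significant result as evidence of no effect. The documents give no equivalence or futility margin that could support this.
- For 400 mg and 100 mg, it states a result on hypotheses that the sequence has not tested on that endpoint.

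At stake is the trial's stated answer to its primary objective. A study meant to find the effective dose range would record, from one missed comparison, that there is no effective dose. The conclusion could also contradict the other regional family, because the two use different endpoints and populations: one could stop at step 1 while the other shows significance for the same doses in the same trial.

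**Working it through.** **Inputs.** Protocol Section 12.1 gives 100 subjects per group, 80% power and a 16-point difference in median percent reduction "between an active dosage group and placebo group, at a 2-sided significance level of 0.05, assuming a standard deviation of 40"%.

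**The plan's own figure.** Normal approximation, treating the 16 points as a difference in means:

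- SE = 40 × √(2/100) = 5.657 points.
- Power = Φ(16/5.657 − 1.960) = Φ(0.868) = 80.7%.
- The sample size formula gives 99 per group.

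The stated 80% with 100 per group is therefore reproduced.

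**What a non-significant 200 mg result can exclude.**

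- 95% CI half-width = 1.960 × 5.657 = 11.09 points. A positive observed difference is non-significant if it is below 11.09.
- The CI contains 16 points if the observed difference is at least 16 − 11.09 = 4.91.
- Both hold for an observed difference from 4.9 to 11.1 points.

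| Observed 200 mg difference | 95% CI (points) | Significant | Contains 16 |
|---|---|---|---|
| 11.0 | −0.1 to 22.1 | no | yes |
| 8.0 | −3.1 to 19.1 | no | yes |
| 3.0 | −8.1 to 14.1 | no | no |
| 0.0 | −11.1 to 11.1 | no | no |

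In the first two rows the protocol would conclude that no dose works, while the data remain compatible with the effect the trial was powered to detect. In the last two rows the design effect is excluded for 200 mg, but smaller effects are not. No row carries a test of 400 mg or 100 mg on this endpoint.

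**What is and is not tested after a stop.** Suppose Section 12.5.1 stops at 200 mg. Section 12.6.2 still compares each dose with placebo on the double-blind responder rate in MITT. Section 12.6.1 still compares each dose on maintenance-phase percent change in MITT-M. Section 12.5.2 runs its own sequence. None of these is stated to depend on the result in Section 12.5.1. The 400 mg and 100 mg doses are thus untested only on the stopped family's primary endpoint.

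**The case against.** The strongest reply is that the sentence sits in a paragraph about type I error and is shorthand for the outcome of the procedure, and that nothing is computed from it. The second half is right: no analysis changes. The first is a charitable reading that the supplied documents do not state, and a prespecified conclusion should say what it means.

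A second reply is that the trigger is improbable. Section 4.4.4 reports a Phase 2a study in which "113 subjects received YKP3089 and 109 received placebo" and which "demonstrated a highly statistically significant effect in favor of the YKP3089 group, 55% vs 21"%, a gap of 34 points. With 100 per arm, a true 34-point effect would be missed with probability Φ(1.960 − 34/5.657) = 0.003% at SD 40. At SD 65 it is about 4%; that SD is roughly the largest compatible with the reported p<0.0001 (34/3.891/√(1/113 + 1/109) = 65.1, approximate because the Phase 2a test is not described). This stands as a reason not to inflate the point. It does not make the rule valid, since the trial was planned for 16 points.

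A third reply is that the missing double-blind SAP may word this correctly. It may. The point is about the protocol text; whether the wording reaches the study report cannot be checked.

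A reader might also infer more than the documents support:

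- That 400 mg and 100 mg would never be tested. Section 12.6 still compares them on secondary endpoints.
- That the results would be lost. Section 12.5.1 plans summary tables of the unranked endpoint, and Section 12.5.2 plans frequencies and percents.
- That the wording causes missed effects. At a true 16 points, step 1 misses in 19.3% of trials (100% − 80.7%), but that follows from the planned power under any wording. Likewise, if 400 mg also had a 16-point effect, it would be nominally significant in about 57% of those misses; that describes the fixed sequence, which is sound.

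**Conclusion.** The prescribed conclusion is wrong as written at all four places. A stop at step 1 supports only that no confirmatory efficacy claim can be made for any dose on that family's primary endpoint. The error is one of inference, not of error control, test order or sample size, but it concerns the primary objective and so should be corrected.

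Its size is shown by the range of 4.9 to 11.1 points, within which a non-significant 200 mg result is still compatible with the 16-point design effect. That range rests on the planning values, on full arms of 100 (Section 12.1 states no dropout allowance), and on a normal approximation for a difference in means. The planned primary test is a rank ANCOVA, for which Section 12.5.1 says effect sizes are not directly estimated, so this interval illustrates the issue and is not a planned output. No planning values are given for the responder family; the same logic applies there without a figure.

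**What to change.** In Sections 12.5.1 and 12.5.2 and in the two synopsis entries, replace the conclusion with: *testing in this family stops and no confirmatory efficacy claim is made for any dose on this primary endpoint; the 400 mg and 100 mg comparisons on this endpoint are reported descriptively.*

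The limit to this primary endpoint is needed; without it the text would conflict with the comparisons in Section 12.6. Leave those secondary analyses as planned, and state that after a stop they are interpreted as non-confirmatory. Check that the double-blind SAP carries the same wording.

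The cost is four sentence replacements and a short statement on interpretation, made by protocol amendment. Section 13.6 sets the procedure: "Protocol Amendments will not be implemented without agreement from the Sponsor", and written IRB approval is also required. With approximately 100 sites in multiple countries (Section 1), that is an administrative burden. Nothing changes in design, sample size, test order, alpha or data collected, and the descriptive summaries are already planned.
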